2.2 Study Endpoint

2.2.1 Primary Study Endpoint and Definition

The primary endpoint of the study is urinary dysfunction in patients within 7 days after catheter removal. In this study, urinary dysfunction was defined as incomplete bladder emptying after the first voiding following catheter removal or an inability to urinate requiring a second catheterization.

Incomplete bladder emptying was characterized by a postvoid residual urine volume (PRUV) exceeding 100 mL (14–18). The residual urine volume in the bladder after the first urination will be estimated immediately following the first urination using bladder ultrasound. The calculation formula is: Bladder urine volume = Anteroposterior diameter * Vertical diameter * Transverse diameter * 0.52. The bladder ultrasound is performed by a fixed radiologist from the ultrasound imaging department, who is exclusively assigned to our department.

The criteria for determining whether secondary catheterization is needed due to difficulty in urination are as follows: 1)The patient is unable to urinate within 10 hours after catheter removal, and percussion of the bladder upper border indicates that it is located above the pubic bone, with an estimated residual urine volume in the bladder greater than 200 ml using bedside bladder ultrasound; 2)Although the patient is able to urinate after catheter removal, they still feel lower abdominal distension after multiple attempts to urinate, and percussion by the physician indicates that the bladder upper border is located above the pubic bone, with an estimated residual urine volume in the bladder greater than 200 ml using bedside bladder ultrasound.

In the determination of the primary endpoint, patients who undergo secondary catheterization for reasons other than urinary retention will also be recorded as primary endpoint events, but sensitivity analysis shall be conducted on these patients in the sensitivity analysis. The specific analysis method is described in the section on sensitivity analysis of the primary endpoint in the statistical analysis. Such events may include the following scenarios:

- 1) The patient requests secondary catheterization due to urgent urination or intense bloating, but the urine volume withdrawn after secondary catheterization does not exceed 100 ml;
- 2) The patient requires secondary catheterization due to disease-related factors (such as secondary surgery, urethral injury, shock, altered consciousness, intestinal obstruction, hemorrhage, transfer to ICU, SOFA score ≥ 2 , etc.).

2.2.2 Secondary study endpoints and definitions.

Secondary endpoints of this study include: 1) Catheter-associated urinary tract infection status; 2) Time to first urination after catheter removal; 3) Grading assessment of catheter-related bladder discomfort (CRBD); 4) Post-catheter removal urinary function evaluation (using ICIQ-SF and IPSS scores); 5) Postoperative complications within 30 days (incidence of complications, types of complications, and grading of complications); 6) Incidence of residual urine volume greater than 200 milliliters after the first urination.

2.2.3 Other indicators and definitions.

Urinary tract infection is defined as an inflammatory response of the urinary epithelium to bacterial invasion. The diagnosis requires both of the following criteria to be met: 1) Urinalysis indicates a bacterial count above the normal upper limit, and 2) Positive urine culture. The time to first urination after catheter removal is defined as the time from the removal of the catheter to the patient's spontaneous urination, measured in hours. The time from the second catheterization to the removal of the urinary catheter is defined as the time interval from the first removal of the urinary catheter to the completion of catheter insertion by the nurse or suprapubic puncture by the ultrasound doctor after the clinician determines that the patient requires a second catheterization.

Complications within 30 days after surgery are assessed according to the Clavien-Dindo classification, and complications of grade II and above are recorded and analyzed. These include, but are not limited to, intraperitoneal bleeding,

gastrointestinal bleeding, anastomotic leak, chylous fistula, surgical site infection (intra-abdominal infection and incisional infection), intestinal obstruction, postoperative diarrhea, pulmonary infection, urinary tract infection, cardiovascular accident, cerebrovascular accident, and thrombotic diseases.

3. Study design.

3.1 Overall study design.

Single-center, prospective, two-arm, parallel-group randomized controlled study.

3.2 Study duration.

This study plans to complete patient enrollment within one year. The postoperative follow-up period for patients is one month. The entire study, including the establishment of the study, patient recruitment, patient follow-up, and data analysis, is expected to last for two years. We will conduct the primary endpoint analysis after all patients have completed their first postoperative month follow-up. The study will begin in February 2024 at the First Hospital of Jilin University.

3.3 Trial flowchart

As shown in Figure 1.

[figure not shown]

Figure 1 Trial flowchart

4. Population.

4.1 Inclusion criteria

- 1) Patients with a confirmed preoperative diagnosis of rectal cancer;
- 2) Preoperative colon CT or rectal MR confirms that the lower edge of the tumor is located in the rectum (including the rectal and anal canal regions) below the

rectosigmoid junction (12 cm from the anal verge);

3) Patients undergoing laparoscopic or robotic-assisted low anterior resection or abdominoperineal resection for rectal cancer.

4.2 Exclusion criteria

1) History of abdominal surgery involving the rectum, sigmoid colon, left hemicolectomy, bladder resection or partial resection, prostate surgery, or hysterectomy.

2) History of urethral injury, cranial surgery, spinal surgery, stroke with limb dysfunction, or Parkinson's disease.

3) Inability to urinate through the urethra preoperatively due to various reasons (e.g., ureteral puncture or ureterostomy).

4) Presence of urinary tract infection preoperatively.

5) Previously diagnosed with bladder overactivity syndrome, urinary retention or voiding dysfunction, or diabetic bladder disease.

6) Concomitant resection of other pelvic organs was performed during surgery, including the bladder, prostate, uterus, cervix, and vagina, except for simple adnexal resection.

7) Lateral lymph node dissection for rectal cancer.

8) Injury to the ureter, bladder, or urethra during the perioperative period.

9) Preoperative renal dysfunction (serum creatinine level $>133 \mu\text{mol/L}$).

10) Emergency surgery.

11) Male patients with preoperative benign prostatic hyperplasia receive medication treatment.

12) Patients with a ureteral stent or ureteral stricture, or bilateral hydronephrosis.

13) Conversion to open surgery.

5. Study treatment groups.

ICCAUT group (Experimental group): Patients underwent laparoscopic or robotic rectal cancer TME surgery, and bladder function exercises were initiated through intermittent catheter clamping at 9:00 am on the first postoperative day, with the urinary catheter removed at 9:00 am on the second postoperative day.

Free-drainage group (Control group): Patients underwent laparoscopic or robotic rectal cancer TME surgery, with the urinary catheter kept open postoperatively, and it was removed at 9:00 am on the second postoperative day.

Physicians need to determine whether to remove the urinary catheter according to the planned date based on a comprehensive assessment of the patient's consciousness, postoperative renal function, circulatory status, and other factors. Using the Sequential Organ Failure Assessment (SOFA) score as a reference, if the patient's SOFA score is less than 2, the catheter will be removed as planned during the day on the second postoperative day. If the SOFA score is 2 or higher, the duration of catheter placement should be extended. The specific situation still requires a comprehensive judgment by the physician. If the catheter is not removed as planned, the reason must be stated in the CRF form. Additionally, if a patient is suspected of having a urinary tract infection during catheter training, the clinical physician may decide to stop the catheter exercise.

5.1 Randomization and group assignment.

5.1.1 Methods for Generating Random Sequences

Patients who meet the inclusion criteria will be randomly assigned to either the bladder training group or the direct removal group. Stratified randomization will be performed based on the following three factors, with randomization information generated using R language on a computer. The stratification factors are: 1) Gender; 2) Whether undergoing abdominoperineal resection (APR). The randomization ratio

between the ICCAUT group and the Free-drainage group is 1:1. A random number table manager (RNTM) ([name]) from the Research Centre of Clinical Epidemiology (RCCE) at Jilin University First Hospital generates and preserves the random number table and allocates the randomization information. The RNTM is independent of other researchers in this trial.

5.1.2 Randomization concealment.

After the random number table is generated through R by RNTM, the random allocation information will be printed on paper strips and placed into opaque envelopes. The random number table and random allocation information will be kept by the RNTM from the RCCE. After clinical doctors and bedside nurses complete the patient screening and determine that a patient meets the inclusion criteria for enrollment, random allocation can be conducted. The random allocation will take place between 6:00 a.m. and 7:00 a.m. on the first day after the patient's surgery, before the intervention procedure. Clinical doctors and bedside nurses will submit an enrollment application to the RNTM and provide the patient's gender information and whether they have undergone an APR surgery. Based on the stratification corresponding to these two factors, the RNTM will deliver the opaque envelopes containing the random allocation information to the bedside nurse before 8:00 a.m. on the first day after surgery. The bedside nurse will then open the envelope and perform corresponding procedures on the patient according to the grouping information inside. The RNTM is independent of other personnel involved in this study, do not participate in any other clinical operations of this study, and have no knowledge of any other information about the patients.

5.2 Blinding and Unblinding.

This study is blinded to the physician group, the ultrasound imaging physicians who assess bladder residual urine volume, and the data analysts. The study group requires patients and assigned nurses to keep the patient's group assignment

confidential from the assigned physicians and bladder ultrasound physicians. Since the clinical operations are performed by the assigned nurses on the patients, this study cannot blind the patients and assigned nurses. The time of unblinding is at the time of patient discharge, and any premature unblinding will be recorded.

6. Study procedure

6.1 Study treatment period.

As shown in Table 1

6.1.1 Patient recruitment and randomization.

1) After admission, patients are initially assessed to determine if they meet the inclusion criteria. If they do, urinalysis and urine culture are performed. The patient's urinary function is evaluated using the International Prostate Symptom Score (IPSS) (Appendix 1) and the International Consultation on Incontinence Questionnaire Short Form (ICIQ-SF) (Appendix 2), and baseline data are collected.

2) Participants will undergo laparoscopic or robotic-assisted radical resection of rectal cancer. For patients with a narrow pelvic cavity or ultra-low rectal tumors scheduled to receive low anterior resection (LAR), either transanal total mesorectal excision (TaTME) or the Turnbull-Cutait pull-through procedure combined with two-stage hand-sewn coloanal anastomosis (TCA) will be employed. The second stage of the TCA procedure will be performed 2 to 3 weeks following the initial operation. All surgeons will be required to perform high ligation of the inferior mesenteric artery (IMA) and to preserve Denonvilliers' fascia. The decision to perform APR will be based on the patient's tumor stage and the outcome of communication between the surgeon and the patient. After surgery, patients are reassessed to determine if they still meet the inclusion criteria and are checked against each exclusion criterion. If they are not excluded, they are deemed suitable for enrollment. The patient is then informed and asked to sign the informed consent. If

the patient is informed and agrees to participate, the informed consent form is signed, and randomization begins. Baseline data and surgical-related data for the enrolled patients are then collected and completed.

3) Based on stratification factors, randomization is conducted on a computer. The randomization information will be delivered to the assigned nurse via an envelope before 8:00 am on the day following surgery. The nurse will then perform the intervention according to the group assignment indicated in the envelope.

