3) Before the urinary catheter is removed on the second day, both groups of patients must complete the CRBD (Catheter-Related Bladder Discomfort) grading assessment again by the assigned nurse (Appendix 3), and urine samples must be collected for urinalysis and urine culture. Additionally, patients in the ICCAUT group must scan a code to fill out the Bladder Training Quality Self-Assessment Form (Appendix 4) before the catheter is first removed. After the catheter is removed, the time from the first catheter removal to the first urination, as well as the volume of the first urination, should be recorded for both groups of patients.

4) Immediately after the first urination, a bladder ultrasound must be performed to assess the residual urine volume in the bladder. The bladder ultrasound is conducted by a fixed radiologist from the ultrasound imaging department, who is exclusively assigned to our department and is located in the same therapeutic area as the patient. After the urinary catheter is removed, the patient must be observed and the situation of any secondary catheterization must be recorded. The observation period is the following 7 days after first urinary catheter removal. For patients who undergo secondary catheterization, the time from the first catheter removal to the secondary catheterization, the volume of urine drained after secondary catheterization, the method of secondary catheterization, and the reason for secondary catheterization must be recorded.

5) Record the IPSS score and ICIQ-SF score of the patient on the day following the first catheter removal (excluding patients who underwent secondary catheterization). Record complications within 30 days after surgery and their Clavien-Dindo classification (Appendix 5).

6.1.3 Discharge and follow-up.

After discharge, when the patient returns for a follow-up visit one month after

surgery, the physician must collect information on complications and their grading within the first postoperative month, and conduct an assessment using the one-month postoperative urinary function score form.

Table 1: Study Enrollment, Intervention, and Outcome Assessment Form

Item	Time point	Study phase		
		Surgery and Recruitment randomization		Post-randomization
		t	n	
Enrollment:				
Screen suitable population			X	
Informed consent			X	
Baseline and surgery-related data collection		X		X
Randomization			X	
Intervention:				
ICCAUT group				X
Free-drainage group				X
Assessment:				

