6.2 Concomitant treatment, follow-up

The total follow-up time for postoperative patients is one month. The follow-up content includes postoperative complications within 30 days, as well as the IPSS and ICIQ-SF scores at one month postoperatively.

The follow-up within the first 30 days after surgery is conducted through in-hospital observation, outpatient visits, phone calls, or questionnaires.

Complications related to the surgery and their grading, as well as the solutions, are recorded during this period

The postoperative chemotherapy regimen for patients will be based on the NCCN 2023 Rectal Cancer Treatment Guidelines, which will guide the appropriate chemotherapy or systemic treatment.

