8.6 Causality assessment

The causality of adverse events with respect to the intervention will be subjectively assessed by the investigator.

9. Data processing and storage

Clinical research data will be recorded through the perioperative eCRF, including perioperative information, pathological data, and follow-up information. To protect patient privacy, patient identification numbers will not be disclosed to data analysts. All patients will be coded and identified using random numbers. These random numbers do not include patient initials or date of birth. Members of the trial steering committee will have a decoding list that specifies the random numbers of patients in the database and their identification numbers.

10. Quality management

The key to the quality control of the trial lies in:

- (1) Blinding quality control

The implementation of blinding in this study may affect the quality of the research, particularly the achievement of the primary endpoint. If the trial is not blinded to surgeons, it may influence their judgment on whether the patient needs secondary catheterization based on whether bladder training was performed. If the ultrasound imaging physicians are not blinded, it may affect their assessment of residual urine volume in the bladder based on their knowledge of the patient's intervention. Therefore, blinding the randomization information from surgeons and ultrasound imaging physicians is one of the key aspects of quality control in this experiment. To this end, the study requires patients and nurses to keep the patient's group assignment confidential from surgeons and ultrasound imaging physicians. Surgeons and ultrasound physicians must also consciously adhere to the principle of not inquiring about the patient's group assignment. Any premature unblinding must be recorded, including the reason and time of unblinding.

(2) Interventional method quality control

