Appendix 5: Postoperative Complications Clavien-Dindo System Grading.

Grading		Definition
I		Postoperative complications that do not require drug, surgical, endoscopic, or radiological intervention, but include drug therapy such as anti-emetics, antipyretics, analgesics, diuretics, electrolytes, physiotherapy, and also include incisional infections that are opened at the bedside;
II		Requires drug therapy, excluding patients who only received Grade I medication, incisional infections requiring antibiotic treatment, and includes blood transfusions and total parenteral nutrition
III		Requires surgical, endoscopic, or radiological intervention
	III a	Does not require general anesthesia
	III b	Requires general anesthesia
IV		Life-threatening complications (including central nervous system complications) requiring IC (intermediate care) or ICU management
	IV a	Organ failure (including dialysis)
	IV b	Multi-organ failure
V		Death

	version 1.1.1	version 1.1.2
2.2.2 Secondary study endpoints and definitions.		The secondary study endpoint is added with 6) Incidence of residual urine volume greater than 200 milliliters after the first urination.
5.1.1 Methods for Generating Random Sequences	The randomly assigned time is on the day when the patient returns to the ward after the operation.	Random assignment will take place between 6:00 am and 7:00 am on the first postoperative day, before the intervention is carried out.
15. Trial organizational structure	This study has no research funding support.	Add a description of whether patients and the public participated in the design of this project and the supervision of project implementation. Add project funding statements.

section	version 1.1.2	version 2.0	Reasons for Revision

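### Protocol section 5.2 ends the blind at each patient's discharge without saying for whom, although the physician still collects and grades 30-day complications afterwards

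*Protocol*

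**What the plan says.** Protocol v2.0 section 5.2 lists who is blinded: "This study is blinded to the physician group, the ultrasound imaging physicians who assess bladder residual urine volume, and the data analysts". Patients and the assigned nurses cannot be blinded. The section then sets the end of the blind: "The time of unblinding is at the time of patient discharge, and any premature unblinding will be recorded". No group is named in that sentence. The same rule stands in section 5.2 of version 1.1.1, so patients enrolled before version 2.0 came under it too.

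Section 6.1.3 describes the visit one month after surgery, following discharge, at which "the physician must collect information on complications and their grading". Section 6.2 says the 30-day follow-up is "conducted through in-hospital observation, outpatient visits, phone calls, or questionnaires".

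Section 2.2.3 says "complications of grade II and above are recorded and analyzed", and its list of complications includes "pulmonary infection, urinary tract infection, cardiovascular accident, cerebrovascular accident, and thrombotic diseases". Appendix 5 defines grade II as follows: "Requires drug therapy, excluding patients who only received Grade I medication".

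The SAP (6.5.3) compares any complication within 30 days, and complications of grade III or above, each with an absolute risk difference and a P value. The SAP does not mention unblinding.

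**The concern.** A blind protects an outcome only if it lasts until that outcome has been assessed. Here it may end, for each patient, before the last assessment by a physician. A physician who knows the arm may ask, test, treat or grade differently.

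The direction of any such effect cannot be known in advance. The protocol's background does give physicians a prior expectation, since it raises the possibility that bladder training leads to more urinary infections. At stake is a secondary endpoint that the SAP reports with a P value. Readers would take its comparison as blinded unless told otherwise.

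**Working it through.** No calculation in the plan bears on this point. The check sets the sections side by side and asks, outcome by outcome, what is still open at discharge.

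**1. Who is unblinded.** Section 5.2 names three blinded groups and then one time point. A reader may take the time point to cover all three. If it includes the data analysts, release of the allocation patient by patient at discharge conflicts with blinding them for an analysis that section 11.7 places after everyone's one-month follow-up. Section 9 withholds patient identification numbers from analysts, and section 16 limits database access during the study. Neither sets a date on which anyone is unblinded.

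**2. Any complication within 30 days.** Events recorded in hospital precede unblinding and are not affected. Events first identified after discharge are collected and graded by the physician (6.1.3), and no section keeps that physician blinded. Grade III and above require an intervention or intensive management, which leaves less room for influence. Grade II, the lowest grade recorded, is defined by drug therapy and so follows a prescribing decision. The exposed part is therefore mainly grade II events first found after discharge, which feed the SAP's any-complication row.

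**3. Urinary tract infection.** Two outcomes need to be kept apart.
- The measure for the secondary objective uses urine collected before catheter removal (6.1.2 item 3; 12.1). That is before discharge, so it is not exposed.
- An infection found later counts as a type of complication. Section 2.2.3 still requires a raised bacterial count and a positive culture, so only the decision to test is open to influence. The SAP gives individual complication types neither an effect size nor a P value.

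**4. Primary endpoint.** The window is 7 days from catheter removal. With removal on schedule on postoperative day 2, it ends on day 2 + 7 = 9. Only a patient discharged before then has any of the window left.
- A first-void residual above 100 ml already makes the endpoint positive, so a later catheterization changes nothing. Only patients with a residual of 100 ml or less, or none measured, remain.
- Catheterization criterion 1 (2.2.1) concerns inability to void within 10 hours of removal. With removal at 9:00 this is settled around 19:00 the same day.
- Criterion 2 could first arise after discharge. It requires reported distension, percussion by the physician and an ultrasound volume above 200 ml.
- Catheterizations for reasons other than retention also count as events, but the planned sensitivity analysis (Protocol 11.4.2.2; SAP 6.5.2.2) recodes them as negative in exactly these patients.

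Exposure is thus effectively limited to criterion 2, in patients discharged within 7 days of removal whose first-void residual was 100 ml or less or not measured.

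**5. Reach of a change.** SAP 2.1 gives 362 enrolled of 400 planned. 400 − 362 = 38, and 38 / 400 = 9.5%.

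**The case against.** The strongest reply is that little is left once the outcomes are separated. The infection measure for the secondary objective precedes unblinding, grade III and above is hard to influence, and the primary endpoint is protected by the early scan, the 200 ml requirement and a sensitivity analysis. This stands, and it limits the point to one secondary endpoint and a narrow part of the primary one.

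A second reply is that section 10(1) gives blinding a different purpose: "If the trial is not blinded to surgeons, it may influence their judgment on whether the patient needs secondary catheterization". Its other reason concerns the ultrasound reading. Both relate to the primary endpoint. A reader might infer that the sponsor also intended complications to be graded blind at one month, but the text does not say so. Keeping the blind longer is good practice, not something section 10(1) already requires.

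Third, section 6.1.3 does not say that the physician at one month belongs to the blinded group, or that this physician is in fact told the arm. This also stands: the plan leaves a risk open and does not establish that bias occurs.

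Fourth, patients know their arm throughout, so a longer blind depends on their silence. That is true, but the trial already relies on the same request during the hospital stay.

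None of these replies supplies a rule that keeps the assessor of 30-day complications blinded.

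**Conclusion.** The gap is real and should be corrected. Section 5.2 does not say who is unblinded, and as written it allows complications first identified after discharge, mainly grade II, to be assessed with knowledge of the arm and to enter a comparison with a P value.

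Two stronger readings are tempting and are not supported. One is that the secondary objective on infection is compromised; its urine sample is taken before catheter removal, and infection as a complication type is not tested. The other is that the primary endpoint is generally unblinded; exposure is confined to the patients described in step 4, and the documents do not say whether any patient is discharged that early.

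No size of bias is claimed, since the documents give neither a discharge day nor a complication rate. The conclusion rests on two assumptions: that unblinding at discharge includes physicians, and that the physician at one month is one of them.

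**What to change.** Amend section 5.2 so that physicians and ultrasound physicians stay blinded until that patient's one-month assessment has been entered, and data analysts until database lock. Record any earlier unblinding with its time and reason, as section 10(1) already asks.

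For patients already unblinded, add one descriptive table by arm:
- complications first identified after discharge, with urinary tract infection on its own line;
- secondary catheterizations after discharge but within 7 days of removal.

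The second item can be taken from the time to secondary catheterization in hours on the CRF (12.1), with the removal and discharge dates. The SAP's categories for that time cannot be used, because they pool everything from 3 days on. The report should say that the table cannot separate a real effect of training from assessment bias.

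The cost is a short amendment and one table, with no added visits or staff. The limits should be stated openly. At SAP 1.0 the amendment reaches only the 38 patients not yet enrolled plus enrolled patients not yet discharged. It relies on patients not disclosing their group, so they need a reminder before the one-month visit. Section 12.1 lists no dates for complications, so dating them may need a check of hospital notes.
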